3.1 Study design

This is a randomised controlled trial using a stepped-wedge random allocation with the following details:

- The environmental hygiene intervention will be rolled out to thirteen hospitals over ten months
- The main intervention – the training of trainers/champions (ToT) will be delivered to selected cleaning champions from three or four hospitals within a certain month (within the same 4 weeks of a specific month in the schedule), hence there will be a total of 4 steps (4 main periods when training happens)
- **The timing allocation for hospitals matched with the four training periods is random**
- The results across unexposed observation periods are compared with that across the exposed observation period
- The stepped-wedge design, with staggered timings for the start of the intervention and intervention length (2 to 8 months), supports feasibility while maintaining the rigour of the study.
- The design allows the NIPH and its partners to work with a group of hospitals at the time to maximise quality and consistency of the implementation, and avoid having to manage the changes across 13 hospitals simultaneously

This is the suitable design to ensure that all the 13 participating hospitals receive the interventions as proposed by NIPH and its partners whilst keeping the rigor of randomisation based on timing.

3.2 Study sites and population

This study will be conducted in thirteen hospitals in three selected provinces in Cambodia. These hospitals have the following characteristics:

- District and provincial referral hospitals in the selected provinces
- Public hospitals
- 46% of them have an operating theatre
- Range of hospital beds: 30 -220
- Ensuring representation in at least three provinces of the country. The three provinces are selected based on a mix of the prior work conducted by WaterAid in those areas, and aiming to select largest referral hospitals in the country. See Table 1 for key characteristics of these provinces

Table 1. Region characteristics

	% rural (vs urban)	Pop density	Income (GDP per capita, 2015)
Kampong Chhnang	85.5%	95	2,726
Battambang	76%	84	2,881
Kratie	90%	34	2,765

Source of information:

http://hdr.undp.org/sites/default/files/nhdr_cambodia.pdf

https://www.nis.gov.kh/nis/Census2019/Provisional%20Population%20Census%202019_English_FINAL.pdf

<https://www.adb.org/sites/default/files/institutional-document/151706/cambodia-country-poverty-analysis-2014.pdf>

In Cambodia, there are twenty-five provinces. Battambang is one of the top seven most populous provinces, which consists of 987,400 people in 2019. Besides a large population, Battambang is a prosperous province for being the leading rice-producing province; it is also an economic corridor that connects Cambodia and Thailand. Kampong Chhnang has 525,932 people living in the province, while there are only 372,825 people situated in Kratie in the same year. With a lesser population, Kampong Chhnang and Kratie are listed among the seven poorer provinces in Cambodia, according to Cambodia Poverty Analysis 2014.

3.3 The intervention

TEACH CLEAN is an intervention aimed at improving environmental hygiene in hospitals in low-resource settings. It was created by the Soapbox Collaborative jointly with NHS Grampian (UK) based on international guidelines for environmental hygiene. It was pilot-tested in The Gambia in 2016 and Tanzania 2018, and used in India and Cameroon among others. Key features include participatory methods and pictorial guidelines to facilitate learning for hospital cleaners, who typically have low education and literacy levels (5,9,10). The CLEAN Frontline study will use the most up to the date version of the package which has been updated recently by the WHO for global roll out. TEACH CLEAN comprises the following stages:

3.3.1 Preparatory stage (phase 1)

This stage includes engagement with hospital managers, selection of facility *cleaning champions* in each hospital; assessment of environmental hygiene status and resources; and adaptation of TEACH CLEAN to the local context.

A situation analysis and basic needs assessment will be conducted to collect necessary data and information for preparation and adaptation of the intervention to the local context – contextualization of the intervention through analysis of relevant policy documents and a rapid facility survey. For the latter, trained surveyors will pay a visit to all the 13 hospitals. During the visit, the surveyors will conduct interviews with hospital and ward leaders responsible for IPC and cleaning, using a semi-structured questionnaire (Appendix 1 – available on request). In addition, a hospital walkthrough will be done to observe the cleaning and hygiene facilities and practices using an observation checklist (Appendix 2- available on request). The collected data will be analysed and the findings will be used to

- identify relevant wards and cleaning champions for the intervention,
- map ward specific sites for environmental swabs (with dipslides) and
- adapt the training tools and process to align with existing policies/guidelines, needs and feasibility, including the feasibility of using digital technologies for the training.

A tailored intervention should optimise bundle implementation and compliance, but such tailoring will not compromise the integrity of the individual components and the ‘sum of the whole’ of the bundle.

3.3.2 Training stage (phase 2)

This stage is primarily a training of facility *cleaning champions* to educate and supervise other existing facility cleaners with environmental hygiene responsibilities – training of trainers (ToT). Cleaning champions are selected on the basis of having a supervisory or senior role within the ward, prior understanding of infection prevention in relation to environmental hygiene, good communication skills and willingness to develop knowledge and take on the role of champion.

The identified facility cleaning champions will be trained as trainers to further train other facility cleaners and staff who are involved in cleaning in the form of training of trainers (ToT). The training content includes as much as possible the seven contextualized modules of TEACH CLEAN training package (CLEAN BOX): i) Introduction to Infection Prevention and Control, ii) Personal hygiene and dress code, iii) Hand hygiene, iv) Personal protective equipment, v) Housekeeping/control of environment, vi) Waste handling, and vii) Linen handling.

The seven TEACH CLEAN training modules cover cleaning agents, frequency of cleaning, cleaning techniques, importance of environmental hygiene for HAI prevention, and, specifically for champions, techniques for supervising staff and methods for attracting sufficient resources. The TEACH CLEAN bundle is currently the only cleaning training for hospitals in resource-limited settings endorsed by several international guidelines including the recent “Best Practices for Environmental Cleaning in Healthcare Facilities: in resourced-limited settings” (7). The CLEAN Frontline study will use the most up to the date version of the package which has been updated recently by the WHO for global roll out.

NIPH in collaboration with DHS will contextualize and deliver the interventions.

The contextualized TEACH CLEAN will be offered primarily to the **three** selected wards identified at the preparatory stage: i) maternity ward, including labour and post-natal rooms, ii) general medicine ward, iv) and paediatric ward.

The timing and duration of the training will be organised with the hospital and ward manager to ensure staff are able to attend whilst maintaining key core personnel in the wards, and to allow for flexibility with staff personal commitments.

3.3.3 Supervision stage (phase 3)

This stage refers to ongoing mentorship by DHS of *cleaning champions* while they educate and supervise existing facility cleaners with environmental hygiene responsibilities. The trained cleaning champions are expected to train other facility cleaners and staff who are involved in cleaning. This requires regular field supervisions and distance support by master trainers to monitor their progress, identify the challenges they face in providing training to other cleaners, and help them address such challenges, including technical support and provision of basic and necessary materials for training and environmental cleaning.

3.4 Evaluation of the intervention and expected outcome

The evaluation aims to ultimately measure the effectiveness of the environmental cleaning bundle (the intervention) in improving the ‘microbiological’ cleanliness of the study hospitals – the primary outcome of the intervention. This expected outcome will not only depend on the package of intervention but also on how the package will be delivered. Crucially, the trial will provide meaningful results about the effect of the training stage (phase 2) and supervision stage (phase 3). The preparatory stage (phase 1) cannot be evaluated as it will commence virtually simultaneously across the hospitals. Therefore, a process evaluation is needed at the training and supervision stage.

3.4.1 Process evaluation

A process evaluation conducted by the Cambodia WaterAid team together with the LSHTM team will aim to capture information around the following aspects of implementation as recommended by the Medical Research Council (UK) guidelines for process evaluations of complex interventions: implementation fidelity, dose, mechanisms, reach and context:

- **Implementation fidelity** will be measured through semi-structured observations of trainings at the ToT level and facility level – we will aim for at least one set of training to be observed in each facility (N=13-26 trainings observed) and using interviews and focus group discussions (FGDs) with stakeholders by an experienced qualitative researcher (see Appendix 3 and Appendix 4). Phone interviews will be conducted with a sample champions and cleaners at regular intervals across the study to assess both implementation fidelity in terms of supportive supervision and contextual changes described just below (See Appendix 3 and Appendix 4).
- With regards to **context**, we will map the hospital characteristics and context (e.g. staffing, size), infection prevention policies and practices (e.g. antimicrobial stewardship, antibiotic use, screening) and other relevant activities (e.g. cleaning staff changes, policy changes) within the hospital in a qualitative way through stakeholders interviews (see Appendix 3). Ongoing reviews of contextual information throughout the intervention at each site will assist with trial site comparisons, replication and scalability and knowledge translation
- **Dose and reach** of the intervention will also be monitored e.g. number of modules delivered, number of facility staff trained, number of supervision sessions. This information will be collected using training records.
- **Data on mechanisms** (e.g. increase in knowledge) through which the intervention is believed to work will also be collected through a quantitative survey enquiring about knowledge, social norms, network structure and self-efficacy measures. See Appendix 5 for the draft survey. The survey will be administered to all staff who cleans in the selected facilities at the end of the trial will allow us to compare knowledge and attitudes scores between control and intervention clusters. This is particularly important to gauge whether the bundle has impacted not only upon behaviour but also on knowledge, which are the longer-term drivers of behavioural outcomes.
- All these data collection tools for the process evaluation have been previously used in the former pilot work of TEACH CLEAN (8).

All process evaluation tools (Appendix 3, 4 and 5) are currently in a draft format and will need to be piloted and refined in an iterative way according to the early qualitative results of the study.

3.4.2 Impact evaluation

[figure not shown]
Randomisation: Hospitals will be randomly allocated to intervention timing 3 months prior to the start of the first training. We will use constrained randomisation to ensure there is a balance in key hospital characteristics in each randomisation step. Specifically, randomisation will be constrained based on region and hospital size using standard methods (11). One of the investigators will be in charge of computer generation of the allocation in terms of time and hospital identifiers. Alternative, we will generate a random allocation using a public method with the key study coordinators (NIPH, WaterAid, DHS and LSHTM) of picking from “a hat” and including all key investigators in this process virtually, but keeping the constrained rules described just above.

During the first month of data collection, i.e. 4 weeks before the start of the first ToT, we will baseline data collection; some intervention aspects of phase 1 of the TEACH CLEAN package will be ongoing

Staff who clean will not be blinded as this is not possible.

Hospital	Period/Month											
	March	May	June	July	August	September	October	November	December	January	February	
0	1	2	3	4	5	6	7	8	9	10		
1 Pilot	0	1	1	1	1	1	1	1	1	1	1	
2 Pilot	0	Training group 1	1	1	1	1	1	1	1	1	1	
3 Pilot	0	1	1	1	1	1	1	1	1	1	1	
4 Pilot	0	0	0	0	1	1	1	1	1	1	1	
5 Pilot	0	0	0	Training group 2	1	1	1	1	1	1	1	
6 Pilot	0	0	0	0	1	1	1	1	1	1	1	
7 Pilot	0	0	0	0	0	1	1	1	1	1	1	
8 Pilot	0	0	0	0	0	Training group 3	1	1	1	1	1	
9 Pilot	0	0	0	0	0	0	1	1	1	1	1	
10 Pilot	0	0	0	0	0	0	1	1	1	1	1	
11 Pilot	0	0	0	0	0	0	0	1	1	1	1	
12 Pilot	0	0	0	0	0	0	0	0	Training group 4	1	1	
13 Pilot	0	0	0	0	0	0	0	0	0	1	1	

Figure 1 – Trial structure

Sampling sites: The unit of measurement for microbiological cleanliness is key hand-touch sites – patient beds and other equipment around the patient area (e.g. beds, equipment trolley, bedside locker) in our study. Formative observation identified these surfaces most frequently touched by healthcare workers, closest to the patient, thus providing the greatest risk of pathogen cross-transmission (12,13). Other studies report these hand-touch sites in hospitals.(7,13)

A picture will be drawn for each ward with the selected surfaces sampled to guide data collection.

Dipslides: are a widely used method for measuring surface microbiological cleanliness, in hospitals and elsewhere (14). We will dipslides coated with a non-specific agar on one side for measuring total Aerobic Colony Counts (ACC/cm²) and a selective agar on the other (Baird-Parker agar, to determine the presence of *S. aureus*; Dimanco, UK). Both sides are applied consecutively to adjacent areas of the sampling site,. Dipslides will be collected from hospitals once a month. They will be transported to local laboratory on the day of collection and incubated in aerobic conditions for 14-36 hours (exact timing will be established after piloting because logistics arrangements can impact on best incubation time) at 37°C. Colonies were enumerated by visual inspection. See Appendix 6 for the laboratory protocol details.

[figure not shown]
Data collection: An independent team (not involved in the delivery of the training) will collect monthly data from pre-agreed hospital sites. The cluster size i.e. number of sites sampled per cluster will be 30 across all wards. The same patient areas will be used in each monthly measurement. Where possible, the sampling week will not be the same each month for the hospital to minimise bias from study participants. If feasible, we will collect information on water and bleach availability, and patient volume at each monthly visit.

Outcome: Proportion of microbiological cleanliness ($<2.5 \text{ cfu/cm}^2 = \text{clean}$; $\geq 2.5 \text{ cfu/cm}^2 = \text{not clean}$) will be calculated for each cluster as the number of sites with $<2.5 \text{ cfu/cm}^2$ out of the 30 sites sampled per period/month.

Power calculations for primary outcome: The intervention will be delivered in four steps across thirteen hospitals (3 hospitals per step; except for one step with 4 hospitals – see Figure 1), with 30 sampling sites each and with a pre-training cleanliness proportion ranging from 30% to 50% will give us over 85% power to detect a 30% relative increase in microbiological cleanliness. This is based on a two-sided 5 % significance level, a two-period decay correlation structure with the following conservative estimates of within- period ICC in microbiological cleanliness at 0.03 (previous pilot), auto-correlation of observation at 0.6 and cluster auto-correlation at 0.6, and the intervention timings shown in Figure 1. The pre- intervention cleanliness proportion, and the within-hospital ICC and were estimated using a pilot data from similar level maternity wards in Tanzania as no local data is available on microbiological cleanliness; other available evidence on levels of microbiological cleanliness confirm in settings with no formal training sow similar levels of hospital cleanliness in low resource settings.(8) We assumed one month delay in the treatment effect for the sample size calculation to allow for champions to train staff in their own facility.

We used the website (<https://clusterrcts.shinyapps.io/rshinyapp/>) and underlying formula operationalised by Hemming et al. (2020).(15) See results in Figure 2.

The power calculations translate **into 4,300 dipslides** (13 hospitals*30 sampling sites*10 months = 3,900 + 10% for contingency purposes)

Figure 2. Sample size calculations

Curve shows the increase in power as the cluster-period size increases (for a fixed number of clusters). Hover cursor over curve to see actual power values

Warning: caution is needed with CRTs with a small number of clusters due to risk of lack of internal and external validity; and appropriateness of calculations used particularly for binary and count outcomes

Parameters:

p0: 0.3 p1: 0.39

Significance level: 0.05

Number clusters per sequence: 1

WP-ICC: 0.03 WP-ICC (lower): 0.01 WP-ICC (upper): 0.05 CAC: 0.602

Individual auto-correlation: 0.6

Data analyses: Aerobic Colony Counts and *S. Aureus* outcomes

- The outcome for unexposed observation periods is compared with that across the exposed observation periods.
- The key independent variable will be the intervention (yes/no). The intervention variable will switch from “no” to “yes” after the first full month of the training
- Characteristics of the individual sites and clusters will be summarised by exposure status so to allow consideration of selection biases and lack of balance.
- These characteristics can be compared by randomisation step. This will include the numbers analysed, the average cluster size, and cluster characteristics
- A few characteristics of the hospital (e.g. size) will be considered as independent variables as these should remain roughly constant throughout the study.
- Each cluster will be analysed according to the actual time when it was “trained” independently on when this was planned for.
- Calendar time is associated with both the exposure to the intervention and also possibly the outcome, and so is a potential confounder and will be adjusted for in the analysis
- Adjusting for the systematically different observation periods and for clustering in the data will be accomplished.
- We will test the residuals of the model to look for autocorrelation over time and will check for influential observations.
- The estimated intra-cluster correlation and time effect from the fitted model will be reported both for use in the design of future trials and to allow appreciation of any underlying confounding effects of calendar time
- We will consider using a small sample correction.

In addition, using the same general model we will create a variable indicating the strength of implementation which we will use as an alternative exposure variable to the simpler *intervention vs control variable*. We will also explore descriptively time trends for each cluster. Finally, we will analyse the knowledge and attitudes descriptively (and by implementation *strength and by microbiological outcomes*) as these measures are only collected at the end of the trial.

Qualitative data from FGDs and observations will be analysed adopting a generalised qualitative approach in which the transcripts were disassembled into low-level descriptive codes and then reassembled into themes that may help explain the observed outcomes

4 Data and reporting

Please refer to our exhaustive data management plan as in Appendix 7. The Consort 2018 extension to stepped wedge randomised trials will be used (16).

5 Ethical approval and consent

Our research team will strictly follow ethical procedures, including the submission of the study protocol and related tools to the National Ethics Committee for Health Research in Cambodia (NECHR) and the ethical review board of LSHTM for review and approval prior to the start. We will also respect the voluntary nature of the participation as well as the confidentiality of the information provided by the participants. Individual informed consent will be sought from the participants prior to data collection. Study information will be posted in all the participating wards (See Appendix 8). The consent forms for each data collection piece are available in the appendices (Appendices 9-11).

6 Quality assurance and risk mitigation

The quality of this study will be ensured by joint efforts of LSHTM and its research partners throughout the whole process of the study, from the study design, preparation of the intervention, implementation and evaluation. All the engagement with hospital staff for the successful completion of the study will follow the principles of Good Clinical Practice. An advisory committee is being established to ensure the study follows the highest standards of research quality.

However, this study may encounter a number of challenges and uncertainties. The COVID-19 pandemic poses extraordinary challenges from the point of view health management and planning. With this mind, we are conscious that, in spite of our best efforts, it might not be feasible to conduct the trial with the timings as intended during national or local lockdowns prohibited. The team behind this study aspires to work together and guided by the Advisory committee adapt to the situation as we go along maintaining where possible the study rigour. Other potential limitations of the study include willingness to participate, participation fatigue, adverse events occurring at the staff, patient or hospital level during the trial, e.g outbreaks of HAIs (COVID-19), seasonal factors, organisational or policy changes. This will be mitigated by frequent monitoring of these in each site. Participating sites will agree to not implement changes that could impact the trial, e.g. cleaning policies or product use, without prior agreement from the study team.

Appendices

- Appendix 1: Questionnaire for interviews with hospital and ward leaders (available on request)
- Appendix 2: Observation checklist for hospital walkthrough (available on request)
- Appendix 3: FGD guide

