### 3.3 Sample size

We calculated that with 30 surface samples in each hospital and with a pre-intervention cleanliness proportion ranging from 30% to 50%, we would have 85% power to detect a 30% relative increase in microbiological cleanliness. This is based on a two-sided 5 % significance level, a two-period decay correlation structure with conservative estimates of within-period intraclass correlation coefficient (ICC) in microbiological cleanliness at 0.03 (previous pilot), observation auto-correlation at 0.6 and cluster auto-correlation at 0.6. The pre-intervention cleanliness proportion and the within-hospital ICC were estimated using pilot data from similar-level maternity wards in Tanzania as no local data was available in Cambodia on microbiological cleanliness. For the power calculations, we used the website (<https://clusterrcts.shinyapps.io/rshinyapp/>) and underlying formula operationalized by Hemming et al. (2020) in March 2021.

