## **4 STATISTICAL PRINCIPLES**

### ***4.1 Confidence intervals and p-values***

We will present 95% confidence intervals and p-values. However, we will not claim significance based on a p-value cut off point. In line with current debates, we will focus on the effect of the intervention, plausible mechanisms via which intervention would work, data quality, study design, bias and the real-world impact, rather than p-values in isolation.

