## 6.2 Analysis methods

For the primary outcome (binary: clean vs not clean) we will use a generalised estimating equation (Stata **xtgee** command) with exchangeable equation structure using sample level data (i.e. surface sampled), accounting for within hospital clustering, with small sample Kauermann-Carroll correction. We will use a binomial distribution and logit link to estimate an odds ratio. Each cluster, hospital, will be analysed according to the actual time when training occurred independently of when training was planned

For all analyses we will adjust for the design factors: stratification variables which are CPA – hospital level - and province, both binary; and calendar time included as a categorical variable in the model). We will also adjust for four a priori potential confounders:

- number of beds per cleaner at the hospital level (linear),
- number of patients on the ward (linear) – time-dependent (monthly measurements)
- temperature of the ward (linear) – time-dependent (monthly measurements)
- surface type (3 categorical levels)

We will use a similar strategy for secondary outcomes. For 2.1 we will use generalized estimating equations again using **xtgee** with a normal distribution and the identity link function.

We will in addition also conduct similar analyses on ward- and hospital-level averages for all outcomes. In these analyses, we will include a single variable which indicated the proportion of samples taken from bed rails (the largest category).

The main results will be presented in a table as follows:

**Table 2** (Shell table). Unadjusted and adjusted primary and secondary outcome results estimating the effect of the intervention on microbiological cleanliness a) clean vs unclean; b) contamination score.

	Unadjusted*	CI	Adjusted**	CI	p-value
Primary (pre-specified) outcome					
Individual samples dataset					
a) Binary clean vs no clean (Unit: odds ratio)					
Exploratory (pre-specified) outcomes					
Individual samples dataset					

b) Contamination score (Unit: number of CFU per displide)					
Hospital/Ward summaries dataset					
a) Binary clean vs no clean (Unit: avg %)					
b) Contamination score (Unit: average CFU per dipslide)					

\*Accounts for clustering, time, and stratification variables

\*\* Accounts for clustering, time, and stratification variables. Adjusted for temperature, patient volume, number of beds per cleaner and surface type.

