TEACH CLEAN will be implemented across all hospitals (13) of three provinces in Cambodia. A stepped wedge randomised trial will be used to evaluate the effectiveness of TEACH CLEAN to improve microbiological cleanliness in Cambodian hospitals. All facilities will receive the intervention. Hospitals are arranged in groups of three or four based on the randomisation with staggered commencement dates of the intervention at four distinct time points. The design will include ten months of data collection. We expect one month gap between the training of champions and the training of staff at the facility level. The main outcome is microbiological cleanliness ($<2.5 \text{ cfu/cm}^2 = \text{clean}$; $\geq 2.5 \text{ cfu/cm}^2 = \text{not clean}$) measured using a non-specific agar on one side for measuring total Aerobic Colony Counts (ACC/cm²). With 30 sampling sites in each hospital and with a pre-training cleanliness proportion ranging from 30% to 50% will give us over 85% power to detect a 10% absolute post-intervention increase in cleanliness.

Evidence from this trial will contribute to future policy and practice guidelines about hospital environmental hygiene and ultimately reduce healthcare associated infections. This would be the first randomised trial on environmental hygiene in low resource settings.

List of abbreviations

AMR	: Antimicrobial Resistance
DHS	: Department of Hospital Services, Ministry of Health
FGD	: Focus Group Discussion
HAI	: Healthcare Associated Infection
IPC	: Infection Prevention and Control
LMICs	: Low- and Middle-Income Countries
LSHTM	: London School of Hygiene and Tropical Medicine
MoH	: Ministry of Health
NECHR	: National Ethics Committee for Health Research
NIPH	: National Institute of Public Health
ToT	: Training of Trainers

1 Background

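### The 85% power belongs to a different analysis: at the 30% baseline used, the SAP's exchangeable GEE with a t reference has about 70%, and the SAP names no reference distribution

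*Combined protocol and SAP*

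**What the plan says.** Protocol section 3.4.2 says the design "will give us over 85% power to detect a 30% relative increase in microbiological cleanliness" across pre-training cleanliness of 30% to 50%. It bases this on "a two-period decay correlation structure with the following conservative estimates". The Figure 2 parameters are p0 0.3, p1 0.39, within-period ICC 0.03 (0.01 to 0.05), cluster auto-correlation 0.602 and individual auto-correlation 0.6. The same section assumes a one-month delay in effect and says of sampling, "The same patient areas will be used in each monthly measurement".

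SAP section 3.3 repeats the claim ("we would have 85% power to detect a 30% relative increase in microbiological cleanliness") with "observation auto-correlation at 0.6 and cluster auto-correlation at 0.6".

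SAP section 6.2 sets the primary analysis as a binomial GEE with logit link, "with exchangeable equation structure using sample level data (i.e. surface sampled), accounting for within hospital clustering, with small sample Kauermann-Carroll correction". Calendar time is categorical, with adjustment for CPA level, province and four confounders. SAP section 4.1 says "We will present 95% confidence intervals and p-values" and declines to use a significance cut-off. No section gives the reference distribution or degrees of freedom.

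The protocol's Executive Summary attaches the same power to another target: "will give us over 85% power to detect a 10% absolute post-intervention increase in cleanliness".

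**The concern.** A power figure should describe the analysis that will be run. Here two things change between calculation and analysis. The exchangeable working correlation is not the assumed decay structure, which costs efficiency though not validity. And 13 clusters call for a t rather than a normal critical value. Kauermann-Carroll repairs the variance estimate; it does not supply the critical value.

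Two things are at stake. If true power at a 30% baseline is near 70%, the chance of missing the target effect is about 30%, not 15%, and an inconclusive result would be over-read. Also, because SAP 4.1 rests interpretation on estimates and intervals, leaving the reference distribution open leaves open whether those intervals have their stated coverage.

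**Working it through.** **Inputs (protocol 3.4.2 and Figure 2).** 13 hospitals in steps of 3, 3, 4, 3; 10 months; 30 sites per hospital-month; p0 0.30, p1 0.39; ICC 0.03; cluster auto-correlation 0.602; individual auto-correlation 0.6. Section 3.1 gives 2 to 8 months of exposure, read as 8, 6, 4, 2 (first exposed in months 3, 5, 7, 9, including the one-month lag).

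**Step 1: reproduce the stated figure.** Covariance of a hospital's monthly proportions:

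V(t,s) = v × [0.03 × 0.602^|t−s| + (0.97/30) × (1 if t = s, otherwise 0.6)]

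with v the average binomial variance: (0.30×0.70 + 0.39×0.61)/2 = 0.224.

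GLS with month effects gives SE = 0.0301 for the 0.09 difference, so 0.09/0.0301 = 2.99.

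- Normal reference: Φ(2.99 − 1.96) = 0.848. Pooled variance gives 0.845 and p0 variance 0.870. The 85% reproduces.
- t(11): T11(2.99 − 2.20) = 0.78. So 85% is a normal-reference figure.

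**Step 2: the planned working correlation, same truth.** The average pairwise correlation within a hospital under this V is 0.0273. Using it as an exchangeable working matrix W, the sandwich variance is

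(ΣX′W⁻¹X)⁻¹ (ΣX′W⁻¹VW⁻¹X) (ΣX′W⁻¹X)⁻¹

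This gives SE = 0.0325, 8% above GLS (0.0325/0.0301), and 0.09/0.0325 = 2.77.

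- Normal reference: Φ(2.77 − 1.96) = 0.79.
- t(11): T11(2.77 − 2.20) = 0.71. With t(9): 0.69.

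The two changes cost about 7 points each: 85% to 78% for the reference, 78% to 71% for the working matrix. The SAP Figure 1 schedule gives about 84% for GLS with z and 70% for the exchangeable analysis with t(11).

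**Step 3: simulation of the logit exchangeable GEE with Kauermann-Carroll.** Correlated binary data matched to these correlations, with month, CPA and province in the model. One simulation (4,000 runs per scenario) gives 71% power with t(11) and 78% with z at 30% to 39%. A second (10,000 runs) gives 67-68% and 75-76%. A third (2,500 runs) gives 71% with t(11).

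With no effect, type I error is about 8% with z (8.2-8.3% in the first simulation) and about 5% with t(11) (5.2-5.5%); with t(9) it is 4.6-5.0%. Coverage of 95% intervals across null and effect scenarios is 91.8-92.9% with z and 94.2-95.3% with t(11).

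**Step 4: by baseline, exchangeable analysis, t(11).**

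| Baseline | 30% relative target: analytic | 30% relative target: first simulation | 10-point target: analytic |
|---|---|---|---|
| 30% | 71% | 71% | 80% |
| 36% | 83% | 83% | not run |
| 38% | 87% | 86% | not run |
| 40% | 90% | 89% | 76% |
| 50% | 98% | 98% | 76% |

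Analytically, 85% is reached at a baseline of 37%. Taking 3 points off for the lower simulation gives about 84% at 38% (86.7 − 3) and 86.5% at 40% (89.5 − 3), hence a threshold of about 37-40%. The second simulation gives 97% at 50%.

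The two targets differ: 30% relative is 9 points at a 30% baseline and 15 points at 50%. For 10 points, the protocol's own GLS gives 91% at 30% and 89% at 40-50%.

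**Step 5: sensitivity at 30% to 39%.**

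| Input varied | GLS, z | Exchangeable, t(11) |
|---|---|---|
| Individual auto-correlation 0 / 0.6 / 0.8 | 74 / 85 / 91% | 61 / 71 / 77% |
| ICC 0.01 / 0.03 / 0.05 | 98 / 85 / 72% | 93 / 71 / 53-55% |
| Individual auto-correlation 0.6, decaying with lag | 78.5% | 53-55% |

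Power rises with the individual auto-correlation, so 0.6 is not conservative unless there is reason to expect a higher value. Re-sampling the same areas makes a positive value plausible, but no source for 0.6 is given.

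**The case against.** Nothing is miscalculated: the protocol names its correlation structure and calculator, the 85% reproduces, and the calculator's own warning about few clusters and binary outcomes is printed. That stands. The fault is a mismatch between calculation and analysis.

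A single figure of 70% would be too precise. The two larger simulations differ by 3 points, more than chance explains. The four confounders were not simulated because the documents give no distributions for them. The result also assumes an individual auto-correlation constant over lags, chosen because it reproduces 85%. The protocol's own ICC range moves power more than the mismatch does. All of this stands, and is why a range should be reported. None of it brings the planned analysis to 85% at the stated inputs: the highest figure is 79%, on a reference with about 8% type I error.

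The shortfall is local under the relative target, and with all eligible hospitals recruited no design change follows. That stands too. But 30% is the baseline in the protocol's own output, and both documents attach the power to the whole 30-50% range. Rejecting p-value cut-offs makes interval coverage matter more, not less.

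Finally, the Executive Summary's claim is true for 10 points under the protocol's own method (89-91%). It is still a different target from the body and SAP, and under it the planned analysis with t(11) stays below 85% at each baseline computed.

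**Conclusion.** The concern holds. At the calculator's own inputs the planned analysis has about 68-71% power with t(11), not 85%. For the 30% relative target the shortfall disappears above a baseline of about 37-40%; for the 10-point target power is 76-80% at 30%, 40% and 50%. Separately, the SAP leaves the reference distribution open, and normal critical values would cost roughly 2 to 3 points of interval coverage.

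This rests on four assumptions: a normal-reference GLS behind the 85%, inferred because it is what reproduces the figure; constant individual auto-correlation over lags; 11 degrees of freedom (t(12) is nearly the same); and no effect on power of the four unsimulated confounders.

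**What to change.** 1. In protocol 3.4.2 and SAP 3.3, restate power for the planned GEE by baseline under the 30% relative target: about 70% at 30%, 86-90% at 40%, 97-98% at 50%. Add sensitivity to the individual auto-correlation (for example 0 to 0.8) and to the ICC range already in Figure 2. Either support calling 0.6 conservative or drop the word.
2. Use one effect target in the Executive Summary, protocol body and SAP, and quote power for that target.
3. In SAP 4.1 or 6.2, state that Kauermann-Carroll 95% intervals and p-values use a t distribution with a stated cluster-level df, for example 13 − 2 = 11. Clusters minus all parameters will not serve. With monthly effects the design-factor model has 1 + 9 + 2 + 1 = 13 parameters (0 df), and the adjusted model 13 + 3 + 2 = 18. If time means the five periods of SAP Figure 1, the counts are 8 (5 df) and 13 (0 df), so the SAP should also say which applies.

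The cost is wording. No hospitals or samples are added. Stated power falls at low baselines, and intervals are 12% wider than with normal critical values (2.20/1.96).
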